10.2. Populations for Analyses

For purposes of analysis, the following analysis sets are defined:

Table IOQV.4. Analysis Sets

Analysis Set	Description
Entered	All participants who signed informed consent
Evaluable	All enrolled subjects with ≥ 2 -week use of unblinded CGM
Safety	All enrolled subjects with any CGM or pen usage

Abbreviation: CGM = continuous glucose monitoring.

10.3. Statistical Analyses

10.3.1. General Statistical Considerations

Statistical analysis of this study will be the responsibility of Lilly or its designee.

Efficacy analyses will be conducted on the evaluable analysis set and safety analyses on the safety analysis set defined in [Table IOQV.4](#).

Given the exploratory nature of the study, the analyses will be primarily descriptive, using descriptive statistics (mean, standard deviation [SD], minimum, median, and maximum for continuous variables; frequency and percentage for categorical variables) or graphs (e.g., scatter plot).

Missed bolus doses and glucose time-in-range will be calculated for Weeks 3-6 for Study Period 1 (blinded CGM) and Weeks 9-12 for Study Period 2 (unblinded CGM).

Any change to the data analysis methods described in the protocol will require an amendment ONLY if it changes a principal feature of the protocol. Any other change to the data analysis methods described in the protocol, and the justification for making the change, will be described in the clinical study report (CSR). Additional exploratory analyses of the data will be conducted as deemed appropriate.

10.3.1.1. Treatment Group Comparability

10.3.1.2. Subject Disposition

The primary reasons for discontinuation will be summarized by study period and subject allocation will be summarized by investigative site for the entered analysis set.

10.3.1.3. Subject Characteristics

Baseline characteristics will be summarized for the entered analysis set and the evaluable analysis set.

10.3.1.4. Treatment Compliance

Amount of useable data from the CGM device and pen will be summarized for the evaluable analysis set.

10.3.2. Efficacy Analyses

10.3.2.1. Primary Analyses

The average number of days per month with a missed bolus dose during the last 3 weeks of Study Period 1 will be summarized. The 3 weeks of data will be adjusted to a 1-month interval, and a 95% confidence interval will be calculated.

10.3.2.2. Secondary Analyses

The percent glucose time-in-range (>70 and ≤ 180 mg/dL) will be calculated and summarized for Study Period 1 and Study Period 2. The number of missed bolus doses (average number of missed bolus doses per day) as well as the percent of missed bolus doses (adjusted to a 1-month interval) will be summarized by Study Period 1 and Study Period 2. The MSBD will be summarized by Study Period 1 and Study Period 2.

10.3.3. Safety Analyses

Adverse events including discontinuations due to AEs and SAEs will be summarized.

10.3.4. Other Analyses

Patient reported outcomes rated on the Likert scale will be summarized using frequency and percentage. Domain or total scores will be summarized using: n, mean, SD, minimum, median, maximum at the times outlined in the SOA ([Table IOQV.1](#)).

In addition, bolus dose, basal insulin dose information, and exposure will be summarized.

10.3.4.1. Subgroup Analyses

The average number of missed bolus doses per month will be summarized for the following baseline subgroups:

- Glucose time-in-range (\leq median vs. $>$ median);
- HbA1c ($\leq 9.0\%$ vs. $>9.0\%$);
- Duration of diabetes (\leq median vs. $>$ median);
- Prior CGM experience (yes vs. no).

Appendix 1. Abbreviations and Definitions

Term	Definition
AE	adverse event: Any untoward medical occurrence in a subject or clinical investigation subject administered a pharmaceutical product that does not necessarily have a causal relationship with this treatment. An AE can therefore be any unfavorable and unintended sign (including an abnormal laboratory finding), symptom, or disease temporally associated with the use of a medicinal (investigational) product, whether or not related to the medicinal (investigational) product.
ALBSS	Adult Low Blood Sugar Survey
BFI	The Big Five Inventory
CGM	continuous glucose monitoring
CIOMS	Council for International Organizations of Medical Sciences
complaint	A complaint is any written, electronic, or oral communication that alleges deficiencies related to the identity, quality, purity, durability, reliability, safety or effectiveness, or performance of a drug or drug delivery system.
compliance	Adherence to all study-related, good clinical practice (GCP), and applicable regulatory requirements.
CRF	case report form
CSR	clinical study report
enroll	The act of assigning a subject to a treatment. Subjects who are enrolled in the study are those who have been assigned to a treatment.
enter	Subjects entered into a study are those who sign the informed consent form directly or through their legally acceptable representatives.
ERB	ethical review board
FOIA	Freedom of Information Act
GCP	good clinical practice
GLSS	General Life Stress Scale
HbA1c	glycated hemoglobin
HCS	Hypoglycemic Confidence Scale
HPSS	Health Problem Solving Scale
IB	Investigator's Brochure

Term	Definition
ICF	informed consent form
ICH	International Council for Harmonisation
Informed consent	A process by which a subject voluntarily confirms his or her willingness to participate in a particular study, after having been informed of all aspects of the study that are relevant to the subject's decision to participate. Informed consent is documented by means of a written, signed and dated informed consent form.
investigational product	A pharmaceutical form of an active ingredient or placebo being tested or used as a reference in a clinical trial, including products already on the market when used or assembled (formulated or packaged) in a way different from the authorized form, or marketed products used for an unauthorized indication, or marketed products used to gain further information about the authorized form.
IOQV	F3Z-MC-IOQV
Malfunction	Any failure of a device to meet its performance specifications or otherwise perform as intended. Performance specifications include all claims made in the labeling for the device. The intended performance of a device refers to the intended use for which the device is labeled or marketed.
MSBD	missing and suboptimal bolus dose
PRISM R II	Pictorial Representation of Illness and Self Measure Revised II
PRO/ePRO	patient-reported outcomes/electronic patient-reported outcomes
SAE	serious adverse event
screen	The act of determining if an individual meets minimum requirements to become part of a pool of potential candidates for participation in a clinical study.
SD	standard deviation
SMBG	self-monitored blood glucose
SOA	Schedule of Activities
SUSARs	suspected unexpected serious adverse reactions
T1D	type 1 diabetes
T2D	type 2 diabetes
UADE	Unanticipated Adverse Device Effect: Any serious adverse effect on health or safety or any life-threatening problem or death caused by, or associated with, a device, if that effect, problem, or death was not previously identified in nature, severity, or degree of incidence in the investigational plan or application (including a supplementary plan or application), or any other unanticipated serious problem associated with a device that relates to the rights, safety, or welfare of subjects.

Term	Definition
US	United States
USPI	United States Package Insert

Appendix 2. Study Governance Considerations

Appendix 2.1. Regulatory and Ethical Considerations, Including the Informed Consent Process

Appendix 2.1.1. Informed Consent

The investigator is responsible for:

- ensuring that the subject or the subject's legal representative understands the nature of the study, the potential risks and benefits of participating in the study, and that their participation is voluntary.
- ensuring that informed consent is given by each subject or legal representative. This includes obtaining the appropriate signatures and dates on the informed consent form (ICF) prior to the performance of any protocol procedures and prior to the administration of investigational product.
- answering any questions the subject or the subject's legal representative may have throughout the study and sharing in a timely manner any new information that may be relevant to the subject's or the subject's legal representative's willingness to continue his or her participation in the study.
- ensuring that a copy of the ICF is provided to the participant or the participant's legal representative and is kept on file.
- ensuring that the medical record includes a statement that written informed consent was obtained before the participant was enrolled in the study and the date the written consent was obtained. The authorized person obtaining the informed consent must also sign the ICF.

Appendix 2.1.2. Recruitment

Lilly is responsible for the central recruitment strategy for subjects. Individual investigators may have additional local requirements or processes.

Appendix 2.1.3. Ethical Review

The investigator or an appropriate local representative must give assurance that the ethical review board (ERB) was properly constituted and convened as required by International Council for Harmonisation (ICH) guidelines and other applicable laws and regulations.

Documentation of ERB approval of the protocol and the ICF must be provided to Lilly before the study may begin at the investigative site(s). Lilly or its representatives must approve the ICF, including any changes made by the ERBs, before it is used at the investigative site(s). All ICFs must be compliant with the ICH guideline on Good Clinical Practice (GCP).

The study site's ERB(s) should be provided with the following:

- the protocol and related amendments and addenda, current Investigator's Brochure, United States Product Information, training checklist, and updates during the course of the study
- the ICF
- other relevant documents (for example, curricula vitae, advertisements)

Appendix 2.1.4. Regulatory Considerations

This study will be conducted in accordance with the protocol and with the:

- consensus ethics principles derived from international ethics guidelines, including the Declaration of Helsinki and Council for International Organizations of Medical Sciences (CIOMS) International Ethical Guidelines
- applicable ICH GCP Guidelines
- applicable laws and regulations

Some of the obligations of the sponsor will be assigned to a third party.

Appendix 2.1.5. Investigator Information

Physicians with a specialty in endocrinology, diabetology, and/or primary care will participate as investigators in this clinical trial.

Appendix 2.1.6. Protocol Signatures

The sponsor's responsible medical officer will approve the protocol, confirming that, to the best of his or her knowledge, the protocol accurately describes the planned design and conduct of the study.

After reading the protocol, each principal investigator will sign the protocol signature page and send a copy of the signed page to a Lilly representative.

Appendix 2.1.7. Final Report Signature

The investigator will sign the final clinical study report (CSR) for this study, indicating agreement with the analyses, results, and conclusions of the report.

The sponsor's responsible medical officer and statistician will approve the final CSR for this study, confirming that, to the best of his or her knowledge, the report accurately describes the conduct and results of the study.

Appendix 2.2. Data Quality Assurance

To ensure accurate, complete, and reliable data, Lilly or its representatives will do the following:

- provide instructional material to the study sites, as appropriate

- sponsor start-up training to instruct the investigators and study coordinators. This training will give instruction on the protocol, the completion of the case report forms (CRFs), and study procedures.
- make periodic visits to the study site
- be available for consultation and stay in contact with the study site personnel by mail, telephone, and/or fax
- review and evaluate CRF data and use standard computer edits to detect errors in data collection
- conduct a quality review of the database

In addition, Lilly or its representatives will periodically check a sample of the subject data recorded against source documents at the study site. The study may be audited by Lilly or its representatives, and/or regulatory agencies at any time. Investigators will be given notice before an audit occurs.

The investigator will keep records of all original source data. This might include laboratory tests, medical records, and clinical notes. If requested, the investigator will provide the sponsor, applicable regulatory agencies, and applicable ERBs with direct access to original source documents.

Appendix 2.2.1. Data Capture System

An electronic data capture system will be used in this study. The site maintains a separate source for the data entered by the site into the sponsor-provided electronic data capture system.

Paper and electronic patient-reported outcomes (ePRO) measures or other data reported directly by the subject are entered into an ePRO instrument at the time that the information is obtained. In these instances where there is no prior written or electronic source data at the site, the ePRO instrument record will serve as the source.

If ePRO records are stored at a third-party site, investigator sites will have continuous access to the source documents during the study and will receive an archival copy at the end of the study for retention.

Any data for which the ePRO instrument record will serve to collect source data will be identified and documented by each site in that site's study file.

Case report form data will be encoded and stored in a clinical trial database.

Case report form data collected by a third party will be encoded by the third party and stored electronically in the third-party's database system. Validated data will subsequently be transferred to the sponsor's data warehouse using standard Lilly file transfer processes.

Any data for which paper documentation provided by the study participant will serve as the source document will be identified and documented by each site in that site's study file. Paper documentation provided by the study participant may include, for example, a paper diary to

collect patient-reported outcomes measures (for example, a rating scale), a daily dosing schedule, or an event diary.

Data from complaint forms submitted to Lilly will be encoded and stored in the global product complaint management system.

Appendix 2.3. Study and Site Closure

Appendix 2.3.1. Discontinuation of Study Sites

Study site participation may be discontinued if Lilly or its designee, the investigator, or the ERB of the study site judges it necessary for medical, safety, regulatory, or other reasons consistent with applicable laws, regulations, and GCP.

Appendix 2.3.2. Discontinuation of the Study

The study will be discontinued if Lilly or its designee judges it necessary for medical, safety, regulatory, or other reasons consistent with applicable laws, regulations, and GCP.

Appendix 3. Classification of Contraceptive Methods

Highly Effective Methods of Contraception:

- Combined oral contraceptive pill and mini-pill
- NuvaRing
- Implantable contraceptives
- Injectable contraceptives (such as Depo-Provera®)
- Intrauterine device (such as Mirena® and ParaGard®)
- Contraceptive patch – ONLY women <198 pounds or 90 kg
- Total Abstinence
- Vasectomy – for men in clinical trials

[figure not shown]
Effective Methods of Contraception (must use combination of 2 methods):

- Male condom with spermicide
- Female condom with spermicide
- Diaphragm with spermicide
- Cervical sponge
- Cervical cap with spermicide

Ineffective Forms of Contraception – not acceptable as a method for clinical trials

- Spermicide alone (please note spermicide alone is not considered a barrier method)
- Immunocontraceptives
- Periodic abstinence
- Fertility awareness (calendar method, temperature method, combination of above 2, cervical mucus, symptothermal)
- Withdrawal
- Post coital douche
- Lactational amenorrhea

Appendix 4. **CCI**

CCI

Appendix 5. Summary of Protocol Amendments

Protocol Amendment 1, Dated 17 Nov 2017

Section	Summary of Changes
2 Schedule of Activities	Negative pregnancy test added as a required activity to be conducted during screening (Visit 1)
6.1 Inclusion Criteria [5b]	Definitions of women of child-bearing potential added to the inclusion criteria
Appendix 3	Classification of contraceptive methods added
Appendix 4 - CCI	Information on CCI and the use of mobile nurses

1. ABBREVIATIONS

AE(s):	Adverse Event(s)
ALBSS:	Adult Low Blood Sugar Survey
APS:	Avoidant Problem Solving
BFI:	Big Five Inventory
CRF:	Case Report Forms
CGM:	Continuous Glucose Monitoring
CSR:	Clinical Study Report
EPS:	Effective Problem Solving
HCS:	Hypoglycemic Confidence Scale
HPSS:	Health Problem Solving Scale
IPS:	Impulsive/Careless Problem Solving
MBD:	Missed Bolus Doses
MSBD:	Missed and Suboptimal Bolus Dose
NMO:	Negative Motivation/Orientation
NTR:	Negative Transfer/Learning
PRISM:	Pictorial Representation of Illness and Self Measure
PRO:	Patient-Reported Outcomes
PMO:	Positive Motivation/Orientation
PTR:	Positive Transfer/Learning
SAE:	Serious Adverse Event
SAP:	Statistical Analysis Plan
SD:	Standard Deviation
T1D:	Type 1 Diabetes
T2D:	Type 2 Diabetes

2. INTRODUCTION

This statistical analysis plan (SAP) details the analyses planned for the data collected during the study F3Z-MC-IOQV(a), an exploratory study sponsored by Eli Lilly and Company, including the definition of analysis populations, derivation of variables, convention of analysis scope, and statistical methodology for evaluation of efficacy and safety of the use of continuous glucose monitoring (CGM) and the insulin injection pen in subjects with type 1 diabetes (T1D) or type 2 diabetes (T2D). Any deviations from this SAP during the actual data analysis will be documented in a statistical analysis change request and when necessary described in the Clinical Study Report (CSR).

3. OBJECTIVES AND ENDPOINTS

3.1 Efficacy Objectives / Endpoints

Objectives	Endpoint(s)
Primary	

 To objectively estimate the average number of days per month with a missed bolus dose in subjects with type 1 or type 2 diabetes with blinded CGM 	
 The average number of days per month with a missed bolus dose
Secondary	

 To estimate the average number of days per month with a missed bolus dose in subjects with type 1 or type 2 diabetes with unblinded CGM To estimate the percent time-in-range in subjects with type 1 or type 2 diabetes with 
 Blinded CGM Unblinded CGM To estimate the percent of missed bolus doses in subjects with type 1 or type 2 diabetes with 
 Blinded CGM Unblinded CGM To estimate the average number of missed bolus doses per day in subjects with type 1 or type 2 diabetes with 
 Blinded CGM Unblinded CGM To estimate the Missed and Suboptimal Bolus Dose (MSBD) in subjects with type 1 or type 2 diabetes with 
 Blinded CGM Unblinded CGM 	
 The average number of days per month with a missed bolus dose Percent time-in-range (glucose >70 and ≤180 mg/dL) Percent of missed bolus doses Average number of missed bolus doses per day The average number of MSBD events per month

Exploratory

- | | |
|--|--|
| 
 • To assess the association between MSBD rate and CGM alert settings • To evaluate characteristics associated with short-term glycemic control in subjects with type 1 or type 2 diabetes • To estimate the average number of days per month with a missed bolus dose in subjects with type 1 diabetes with 
 ○ Blinded CGM ○ Unblinded CGM • To estimate the average number of days per month with a missed bolus dose in subjects with type 2 diabetes with 
 ○ Blinded CGM ○ Unblinded CGM | 
 • Correlation between MSBD rate and CGM alert settings • Outcome for each PRO instrument* • The average number of days per month with a missed bolus dose • The average number of days per month with a missed bolus dose |
|--|--|
-

Abbreviations: CGM = continuous glucose monitoring; PRO = patient-reported outcomes.

* if available for use

3.2 Safety Endpoints

The safety endpoints include:

- Adverse events,
- Local laboratory test for HbA1c.

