9.4. Safety

9.4.1. Laboratory Tests

For each subject, the local laboratory test for HbA1c should be conducted according to the SOA (Table IOQV.1). A pregnancy test may be performed at the investigator's discretion if there is suspicion of possible pregnancy.

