5.3 Safety Analysis Set

The safety analysis set comprises all entered subjects with any CGM or pen usage. All safety analyses will be performed on this analysis set.

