9. ANALYSIS OF SAFETY ENDPOINTS

All safety summaries are to be performed on the safety analysis set by period, unless stated otherwise.

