10.4 Glycated Hemoglobin (HbA1c) Results

The HbA1c results (%) at each scheduled visit will be summarized by descriptive statistics.

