11. LIST OF TABLES AND DATA LISTINGS

11.1 Statistical Tables

The statistical tables will be generated using SAS[®] version 9.4. The sample size (n) and frequency (count) will be presented by whole number. The mean, standard deviation, median, minimum, and maximum will be rounded to one decimal place. The percentage will be presented to one decimal place.

Number	Title	Population
14.1.1	Subject Disposition	Screened
14.1.2.1	Demographics and Baseline Characteristics	Entered

Number	Title	Population
14.1.2.2	Demographics and Baseline Characteristics	Evaluable
14.1.3.1	Medical History	Entered
14.1.3.2	Medical History	Evaluable
14.1.4.1	Diabetes Diagnosis	Entered
14.1.4.2	Diabetes Diagnosis	Evaluable
14.1.5.1	Big Five Inventory	Entered
14.1.5.2	Big Five Inventory	Evaluable
14.1.6	Treatment Compliance	Evaluable
14.2.1*	Missed Bolus Dose	Evaluable
14.2.2.1.1	Number of Missed Bolus Doses per Month by HbA1c	Evaluable
14.2.2.1.2	Number of Missed Bolus Doses per Month by Duration of Diabetes	Evaluable
14.2.2.2	Percent Time-in-Range of Glucose	Evaluable
14.2.2.3	Missed or Suboptimal Bolus Dose	Evaluable
14.2.2.4	Glycated Hemoglobin (HbA1c) Results	Evaluable
14.2.3.1	Hypoglycemic Confidence Scale (HCS)	Evaluable
14.2.3.2	Adult Low Blood Sugar Survey (ALBSS)	Evaluable
14.2.3.3	Health Problem Solving Scale (HPSS)	Evaluable
14.2.3.4	Pictorial Representation of Illness and Self Measure (PRISM)	Evaluable
14.2.3.5	General Life Stress Scale (GLSS)	Evaluable
14.2.3.6.1	Number of Days per Month with Missed Bolus Dose in Subjects with Type 1 Diabetes	Evaluable
14.2.3.6.2	Number of Days per Month with Missed Bolus Dose in Subjects with Type 2 Diabetes	Evaluable
14.3.1.1	Number of Subjects with Adverse Events	Safety
14.3.1.2	Number of Adverse Events	Safety
14.3.1.3	Number of Subjects with Adverse Events by MedDRA System Organ Class / Preferred Term	Safety
14.3.1.4	Number of Subjects with Adverse Events by MedDRA System Organ Class / Preferred Term and Severity	Safety
14.3.1.5	Number of Subjects with Insulin Related Adverse Events by MedDRA System Organ Class / Preferred Term	Safety
14.3.1.6	Number of Subjects with Pen Related Adverse Events by MedDRA System Organ Class / Preferred Term	Safety
14.3.1.7	Number of Subjects with CGM Related Adverse Events by MedDRA System Organ Class / Preferred Term	Safety
14.3.1.8	List of Adverse Events Leading to Withdrawal from the Study	Safety
14.3.1.9	List of Serious Adverse Events	Safety
14.3.1.10	List of Death (if there is any)	Safety

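### HbA1c is a declared safety endpoint, but its only results table uses the evaluable set, so treated subjects who leave before about Week 8 are left out of the summary

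*SAP*

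**What the plan says.** **Role of HbA1c.** SAP 3.2 lists two safety endpoints: adverse events and "Local laboratory test for HbA1c". Protocol 9.4.1, under the Safety heading, says "For each subject, the local laboratory test for HbA1c should be conducted according to the SOA". HbA1c is not among the efficacy objectives or endpoints in SAP 3.1 or in Protocol Table IOQV.2.

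**Population for safety.** SAP 5.3 defines the set: "The safety analysis set comprises all entered subjects with any CGM or pen usage". It adds: "All safety analyses will be performed on this analysis set". Protocol 10.3.1 agrees: "Efficacy analyses will be conducted on the evaluable analysis set and safety analyses on the safety analysis set". SAP 9 repeats the rule with a qualifier: "All safety summaries are to be performed on the safety analysis set by period, unless stated otherwise".

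**What is planned for HbA1c.** SAP 9, the safety section, contains no HbA1c analysis. The analysis is in SAP 10.4, within the efficacy section: "The HbA1c results (%) at each scheduled visit will be summarized by descriptive statistics". SAP 10 opens by putting its summaries on the evaluable set. In SAP 11.1, Table 14.2.2.4, titled "Glycated Hemoglobin (HbA1c) Results", is assigned to the evaluable population. None of the 14.3 safety tables covers HbA1c.

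**Collection.** The schedule in both documents draws HbA1c at Visit 1, Visit 3 (Week 6), Visit 5 (Week 12) and Early D/C.

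**The concern.** One of the two declared safety endpoints has no summary on the set that the plan reserves for safety. This matters because of what defines the evaluable set. SAP 5.2 requires at least 2 weeks of unblinded CGM, so a subject qualifies only by staying into Period 2 and wearing the device there. For a safety measure that filter is a poor one. Those who stop early may differ in glycaemic control from those who stay, and a table confined to the stayers cannot show it. The Early D/C draw is made on subjects who leave, and for those who leave before qualifying, the value cannot enter the summary table.

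**Working it through.** **1. When a subject can become evaluable.** Protocol 5.1.3 unblinds the CGM after the Visit 3 assessments at Week 6. SAP 5.2 asks for 2 weeks of unblinded use. Earliest qualification: 6 + 2 = Week 8, approximately, given visit windows of 3 days either way.

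**2. Who is summarised.** For a subject with some CGM or pen use:

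| Time of leaving | Post-baseline HbA1c the schedule provides | In safety set | In Table 14.2.2.4 |
|---|---|---|---|
| Before Week 6 | Early D/C | Yes | No |
| Week 6 to about Week 8 | Week 6 and Early D/C | Yes | No |
| After about Week 8, with 2 weeks of unblinded use | Week 6 and Early D/C | Yes | Yes; handling of the Early D/C value not stated |
| Completes, with 2 weeks of unblinded use | Week 6 and Week 12 | Yes | Yes |

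The first two rows are the gap. It follows from the population label alone and does not depend on how a scheduled visit is defined.

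**3. The plan's own figure.** SAP 4.1 expects 80 screened from 68 subjects and a 15% screen-fail rate: 68 / (1 − 0.15) = 80.0. This reproduces. The target of 50 rests on no power or precision formula, so nothing further can be reproduced.

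**4. Ceiling on subjects left out.** Protocol 5.2 plans about 68 enrolled and about 50 evaluable; SAP 4.1 plans 68 entered and 50 completers. The shortfall is 68 − 50 = 18, and 18 / 68 = 26.5%.

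**5. Range.** The documents do not say when dropouts occur. Let f be the assumed share of the 18 who leave before about Week 8. The number omitted is 18 × f, and the proportion is 18 × f / 68.

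| f (assumed) | Subjects omitted | Share of 68 |
|---|---|---|
| 25% | 4.5 | 6.6% |
| 50% | 9 | 13.2% |
| 75% | 13.5 | 19.9% |
| 100% | 18 | 26.5% |

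**6. Other outputs that carry HbA1c.** SAP 8.2 counts baseline HbA1c categories on the entered and evaluable sets. Table 14.2.2.1.1 uses HbA1c only to form subgroups. Listing 16.2.6.2.2 gives individual results with no population stated. None of these summarises on-study HbA1c in the safety set.

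**The case against.** The strongest defence is that this is a labelling matter in a small, single-arm, descriptive study. Protocol 10.3.3 names only adverse events, related discontinuations and SAEs as safety analyses, no objective concerns HbA1c, and no decision turns on it. The closing clause of the SAP 9 rule allows exceptions, and the Evaluable label could be read as one. Individual values may be listed, and Listing 16.2.3 identifies the subjects excluded from the evaluable population.

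Part of this stands. The consequence is small, and the inconsistency could also be removed by relabelling HbA1c in SAP 3.2. The exception clause is weak cover, however: it governs a section that never mentions HbA1c, while SAP 5.3 and Protocol 10.3.1 carry no such clause and no reason is given for departing from them. A listing is not a summary.

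Three stronger readings are tempting, and the documents do not support them:

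- **That the wording of SAP 10.4 excludes Early D/C values.** Early D/C is a column in the SAP's own schedule table in 4.2, with HbA1c marked. The SAP does not say whether it counts as a scheduled visit. SAP 10 substitutes the early-termination date only when setting the CGM and pen data window. The fault is a missing rule, not a stated exclusion.
- **That early leavers' HbA1c is absent from the report.** It is absent from the summary table. Listing 16.2.6.2.2 may still show it.
- **That about a quarter of the HbA1c data is lost.** The 18 is a ceiling on subjects, not a count of lost post-baseline values. A subject lost to follow-up may have no Early D/C draw. A subject who consented but never used the CGM or pen is in neither set, so changing the population would not bring that subject in.

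**Conclusion.** The SAP contradicts itself on the population for HbA1c. Followed as written, the only HbA1c results summary omits every subject with CGM or pen use who leaves before about Week 8, including any who have a Week 6 or Early D/C value. Under the planned numbers at most 18 of 68 subjects (26.5%) are affected. That ceiling assumes that the whole planned shortfall used a study device and left before qualifying; if a quarter to three quarters of the 18 left that early, the figure is about 4.5 to 13.5 subjects (6.6% to 19.9%). How many post-baseline HbA1c values this represents cannot be worked out from the documents. It is a minor point: it does not touch the primary estimate, and it is worth correcting mainly because the correction is so cheap.

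**What to change.** Produce Table 14.2.2.4 on the safety set. Keep the evaluable-set version as a second panel if it is wanted beside the efficacy results. Amend SAP 10.4 and the population column in SAP 11.1 to match, and add one sentence on how Early D/C values are presented. A row of their own would serve, since merging them with Week 6 or Week 12 would mix values taken at different times.

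The minimum alternative is to reclassify HbA1c in SAP 3.2 as an efficacy or exploratory measure and give the reason. That removes the contradiction within the SAP, but it leaves early leavers out of the summary, and Protocol 9.4.1 would still place the test under Safety.

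Cost: one extra panel and a short SAP correction. The schedule already collects the data, and no visit or procedure changes.
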